Study Design	 within 3 months within 12 months Incidence of a MaxTack[™] Motorized Fixation device deficiency (DD) (e.g., insufficient tack penetration, loose tacks, tack(s) migration, tacker battery issue, etc.) on the day of the index procedure. Operative time for mesh fixation, defined as the time elapsed from the initiation of the mesh fixation process with MaxTack[™] to its completion. Surgeon satisfaction as assessed by Surgeon Satisfaction Questionnaire postoperatively. Length of hospital stay after minimally invasive ventral hernia repair procedure where the MaxTack[™] Motorized Fixation Device was used for fixation. Change in subject-reported pain at the hernia site evaluated with Numeric Rating Scale (NRS) score from 0 to 10 at screening and compared to the following timepoints: at Month 1 at Month 12 Change in subject Quality of life (QoL), as measured through the administration of the Hernia Quality of Life (HerQLes) questionnaire, evaluated at screening and compared to the following timepoints: at Month 1
	performance and safety of the MaxTack [™] Motorized Fixation Device used for fixation in minimally invasive ventral hernia repair procedures. The study will be conducted at approximately 10 sites within the United States. However, additional sites in other regions may be added as needed to meet study objectives.
	Upon obtaining IRB/EC approvals, subjects who have signed an informed consent form and who meet eligibility criteria will be enrolled in the study. Subjects will undergo elective minimally invasive ventral hernia repair

AFFIX (MaxTack [™] Motorized Fixation Device) Clinical Investigation Plan				
MDT23014	Revision	3.0	Page 15 of 97	Medtronic
	surgery using mesh for reinforcement. The procedure will utilize the MaxTack [™] Motorized Fixation Device for mesh fixation and evaluations will be conducted at various time points, including Screening, Operative, Discharge, and postoperative visits at Month 1, Month 3, and Month 12.			
	The study duration is estimated to be approximately 13 months of recruitment followed by a 12-month postoperative follow-up period (+ 45 Days). The primary analysis will be conducted when all subjects have completed their Month 3 follow-up visits (or exited the study) and may be used for regulatory and publication purposes. The final analysis, intended for comprehensive assessment, will be conducted when all subjects have completed their Month 12 follow-up visit and / or exited the study.			

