5.2.2 Secondary Endpoints

The secondary endpoints will include:

- Incidence of Surgical Site Occurrence (SSO) which are the following Adverse Events (AEs) related to the study device, mesh, and / or study procedure and defined as Seroma, Hematoma, Surgical Site Infection (SSI), bleeding at tack implantation site following the MaxTack[™] Motorized Fixation Device used for fixation in minimally invasive ventral hernia repair procedures at the following timepoints:
 - by Discharge
 - o within 1 month
 - within 3 months
 - within 12 months
- Incidence of SSO requiring Procedural Intervention (SSOPI), which are the following AEs related to the study device, mesh, and/or study procedure and defined as Seroma, Hematoma, Surgical Site Infection, bleeding at tack implantation site following the MaxTack[™] Motorized Fixation Device used for fixation in minimally invasive ventral hernia repair procedures at the following timepoints:
 - by Discharge
 - o within 1 month
 - o within 3 months
 - o within 12 months
- Incidence of hernia recurrence following the MaxTack[™] Motorized Fixation Device used for fixation in minimally invasive ventral hernia repair procedures. The evaluation of hernia recurrence will be performed via a Valsalva maneuver during a physical examination and confirmed per site standard of care medical imaging, if necessary, at the following timepoints:
 - \circ within 1 month
 - o within 12 months
- Incidence of hernia recurrences resulting in reoperation, defined as an operative procedure performed with the specific goal of repairing the recurrent hernia, at the following timepoints:

- o within 1 month
- \circ within 3 months
- within 12 months
- Incidence of MaxTack[™] Motorized Fixation Device deficiencies (e.g., insufficient tack penetration, loose tacks, tack(s) migration, tacker issue battery etc.) on day of the index procedure.
- Operative time for mesh fixation, defined as the time elapsed from the initiation of the mesh fixation process with MaxTack[™] to its completion
 - Surgeon satisfaction as assessed by Surgeon Satisfaction Questionnaire postoperatively.
 - Length of hospital stay after minimally invasive ventral hernia repair procedure where the MaxTack[™] Motorized Fixation Device was used for fixation.
- Change in subject-reported pain at the hernia site evaluated with Numeric Rating Scale (NRS) score from 0 to 10 at screening and compared to the following timepoints:
 - o at Month 1
 - o at Month 3
 - o at Month 12

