11.4 Risk-Benefit Rationale

As described in the IFU for the MaxTack[™] Motorized Fixation Device, a ventral hernia repair procedure involving a tacker involves risk. These complications are associated with both the procedure itself as well as the devices being used. For patients who are candidates for the study, the benefits of using the MaxTack[™] Motorized Fixation Device during their hernia repair procedure may outweigh these risks.

In conclusion, the MaxTack[™] Motorized Fixation Device has been shown to have a favorable benefit-risk profile based on the criteria of the target population and the risks and benefits potentials of the device.

12. Adverse Events and Device Deficiencies

For enrolled subjects, adverse events (AE) and device deficiencies (DD) will be collected from the time of skin incision until the subject exits. If an AE is considered unresolvable by the investigator, it will be documented within the eCRF that the AE remains unresolved or unrecovered at the time of study exit. Initial reporting of AEs or DDs may be done by phone, email, or by completing as much information as possible on the appropriate eCRF. The completed AE or DD eCRF must be submitted to Medtronic as soon as possible.

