12.2 Device Deficiency

The device deficiency (DD) definition is provided in Table 5: Adverse Event and Device Deficiency Definitions. DD information will be collected throughout the study and reported to Medtronic. Note that a DD that resulted in an AE to the subject should be captured as an AE only.

AFFIX (MaxTack [™] Motorized Fixation Device) Clinical Investigation Plan				
MDT23014	Revision	3.0	Page 50 of 97	Medtronic

In the event of a DD, the device should be returned to Medtronic for analysis, if possible. Instructions for returning the study device will be provided. Device deficiencies should also be documented in the subject's medical record.

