Serious Adverse Device Effect (SADE) (ISO14155:2020, 3.44)	Adverse device ef characteristic of a		has resulted in any of adverse event.	the consequences	
Device Deficiency (DD) (ISO14155:2020, 3.19)	durability, reliabili NOTE 1: Device de inadequacy in the labeling. NOTE 2: This defir	ity, usabi eficiencie informa nition inc	evice with respect to it ility, safety, or perform is include malfunctions tion supplied by the m ludes device deficienci vice or the comparator	ance. s, use errors, and anufacturer including es related to the	
Serious Health Threat (SHT) (ISO14155:2020, 3.46)	imminent risk of d users or other per subjects, users or NOTE 1: This woul nature such that t	leath or a sons, an other pe ld include hey becc	d that requires prompt rsons. e events that are of sig	in the health in subjects, remedial action for other nificant and unexpected ential serious health hazard	
Relatedness					
investigators will use th	Each AE will be classified according to four different levels of causality. The sponsor and the investigators will use the following definitions to assess the relationship of the AE to the MaxTack™ motorized fixation device, mesh, or study procedure. For purposes of analysis categories considered "related" will include Possible, Probable and Causal.				
Not Related	or proced the event (if the respination implausib the discor level of activation creintroduc activation the event affected b the event concurrent	has no t ure does no ponse pa le ntinuatio ctivation, ction of i /exposu involves oy the de can be a at illness,	emporal relationship w t follow a known respo attern is previously kno n of device application dexposure - when clinic ts use (or increase of the re), do not impact on the a body-site or an orga vice or procedure ttributed to another ca	or the reduction of the cally feasible – and he level of he event	

AFFIX (MaxTac Clinical Investi				
MDT23014	Revision	3.0	Page 52 of 97	Medtronic

	 the event does not depend on a false result given by the device used for diagnosis, when applicable In order to establish the non-relatedness, not all the criteria listed above might be met at the same time, depending on the type of device/procedures and the event. The relationship is weak but cannot be ruled out completely. Alternative 					

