Possible	causes are also possible (e.g., an underlying or concurrent illness/ clinical condition or/and an effect of another device, drug or treatment). Cases where relatedness cannot be assessed or no information has been obtained should also be classified as possible.					
Probable	The relationship seems relevant and/or the event cannot reasonably be explained by another cause.					
Causal Relationship	 The event is associated beyond reasonable doubt when: the event is a known side effect of the product category the device belongs to or of similar devices and procedures the event has a temporal relationship with device use/application or procedures the event involves a body-site or organ that the event involves a body-site or organ that the device or procedures are applied to the device or procedures have an effect on the event follows a known response pattern to the device (if the response pattern is previously known) the discontinuation of device application (or reduction of the level of activation/exposure) and reintroduction of its use (or increase of the level of activation/exposure), impact on the event (when clinically feasible) other possible causes (e.g., an underlying or concurrent illness/ clinical condition or/and an effect of another device, drug or treatment) have been adequately ruled out harm to the subject is due to error in use the event depends on a false result given by the device used for diagnosis, when applicable In order to establish the relatedness, not all the criteria listed above might be met at the same time, depending on the type of device/procedures and the event. 					
Unavoidable Adverse Events (UAE)	For study purposes, the following unavoidable adverse event (UAE) occurrences are considered to be expected observations following surgical procedures (primarily associated with anesthesia) and will not be considered reportable AEs, as long as the event is not associated with significant sequelae, does not prolong hospitalization, and responds to standard medical therapy:					

AFFIX (MaxTac Clinical Investig		d Fixa	tion Device)			
MDT23014	Revision	3.0	Page 53 of 97	Medtronic		

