	 Postoperative transient nausea determined to be procedure related within the first 24 postoperative hours. Postoperative transient emesis determined to be procedure related within the first 24 postoperative hours. Postoperative constipation determined to be procedure and/or medication related for the duration of medication administration for management of pain. Postoperative pain that the Investigator considers common and within normal limits for the procedure and is well-managed with medication. 					
	Device/	Procedu	re Relatedness			
Study Device Related	An AE that results from the presence or performance (intended or otherwise) of the MaxTack™ Motorized Fixation Device.					
Mesh Related	An AE that results from the presence or performance (intended or otherwise) of the mesh.					
Study Procedure Related	fixation methods,	, skin clo	sure, etc.) related to t	nesthesia, incision, other he implantation or surgical ion Device, or the mesh.		

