12.4 Reporting of Adverse Events and Device Deficiencies

Investigators should assess and report the appropriate information on the AE eCRF for the following events, starting from the point of skin incision until the subject exits the study:

- o All AEs related to the MaxTack[™] Motorized Fixation Device, mesh, or study procedure
- o All events that lead to death, regardless of relatedness
- Any non-subject adverse event

Reporting requirements are noted in Section 12.3.1. Assessment of events will include date of event, relationship to study device, relationship to mesh, relationship to study procedure, description, seriousness, action(s) taken, date of resolution and outcome. Additionally, any medication/treatment administered to resolve an AE must also be reported.

Subject Status AE Reporting		AEs to Report Timeframe		
	Required			
Preoperative Screen failure	No	N/A		
Intraoperative Screen failure	No	N/A		
Enrolled	Yes	From skin incision through Study Exit (e.g., study completion, withdrawal or LTFU)		

 Table 7: Subject Status Adverse Event Reporting

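### Section 12.2 sends device deficiencies that led to a subject AE to the AE record only, so the index-day deficiency endpoint may leave them out

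*Protocol*

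**What the plan says.** The Synopsis and Section 5.2.2 both list the incidence of MaxTack device deficiencies as a secondary endpoint. Section 5.2.2 gives as examples "insufficient tack penetration, loose tacks, tack(s) migration, tacker issue battery etc.) on day of the index procedure"; the Synopsis limits the endpoint to the same day ("tacker battery issue, etc.) on the day of the index procedure"). Neither place excludes a deficiency because an AE followed.

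The opening of Section 12 treats AEs and DDs as separate records: "The completed AE or DD eCRF must be submitted to Medtronic as soon as possible". Section 12.2 then sets the capture rule: "Note that a DD that resulted in an AE to the subject should be captured as an AE only".

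Section 12.4 says what is assessed for an AE. Besides the date of the event, the items include "relationship to study device, relationship to mesh, relationship to study procedure, description, seriousness, action(s) taken", followed by resolution date and outcome. Section 14.5 says secondary endpoints are summarised descriptively on the full analysis set, and does not name the records from which the DD endpoint is drawn.

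**The concern.** The endpoint is defined by what happened to the device. The capture rule sorts the same events by what happened to the subject. A deficiency that caused an AE belongs to the endpoint but, under Section 12.2, is not kept as a DD.

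The protocol itself expects deficiencies to cause AEs. Section 6.1 reasons that a tack failure or deficiency may show itself as a hernia recurrence within 3 months. Section 11.1 links insufficient holding force to tack or mesh migration, adhesions, erosion and recurrence. Loose tacks, tack migration and insufficient penetration are the endpoint's own examples.

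At stake is the only listed secondary endpoint that counts device deficiencies, in a study whose data may be used for regulatory and publication purposes (Section 4.2). An incidence taken from DD forms alone could understate the rate by leaving out the deficiencies that mattered to subjects.

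**Working it through.** The protocol states no figure for this endpoint, so there is none to reproduce. The check compares the passages and then illustrates the possible size.

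**1. Can the missing cases be identified from the AE record?**

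- *Deficiency marker.* The AE items in Section 12.4 include none.
- *Date.* The only onset date listed is that of the event. If the AE appears after surgery, its date does not place the underlying deficiency on the index day.
- *Device-relatedness as a substitute.* It is too wide. A study-device-related AE is "An AE that results from the presence or performance (intended or otherwise) of the MaxTack" device, so it covers a device that worked as designed. The categories counted as related "will include Possible, Probable and Causal", and the lowest of these also takes in cases without information: "Cases where relatedness cannot be assessed or no information has been obtained should also be classified as possible".

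DD forms alone can therefore undercount, while DD forms plus all device-related AEs can overcount.

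**2. Which deficiencies are unaffected?** Those without a subject AE stay on the DD record. This includes deficiencies with potential for a serious adverse device effect, which Section 12.4.1 classifies separately.

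**3. Size of a possible undercount.**

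Inputs: 110 planned subjects (Section 14.6). The only DD figure in the document is no deficiencies in the ReliaTack study, with 40 subjects in its ventral arm (Appendix I). That is a different device.

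- One omitted subject: 1/110 = 0.91 percentage points.
- Clopper-Pearson upper 95% limit for 0/40: 1 − 0.025^(1/40) = 8.81%. Applied to 110 subjects: 0.0881 × 110 = 9.7, so up to about 9 subjects.

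The counts below are assumptions within that range.

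| Subjects with a true index-day DD | Recorded as AE only | True incidence (95% CI) | Incidence from DD records (95% CI) |
|---|---|---|---|
| 2 | 1 | 2/110 = 1.8% (0.2–6.4) | 1/110 = 0.9% (0.0–5.0) |
| 9 | 1 | 9/110 = 8.2% (3.8–15.0) | 8/110 = 7.3% (3.2–13.8) |
| 9 | 2 | 8.2% (3.8–15.0) | 7/110 = 6.4% (2.6–12.7) |
| 9 | 4 | 8.2% (3.8–15.0) | 5/110 = 4.5% (1.5–10.3) |

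**4. Size of the opposite error.** Appendix I reports 5 AbsorbaTack-related AEs among 54 subjects. At that rate, 5/54 × 110 = 10.2 device-related AEs would be expected here. None of the AE terms listed for those five events names a malfunction, so counting every device-related AE as a deficiency would add events that are not deficiencies.

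**The case against.** The strongest reply is that the harm depends on a derivation the protocol never states. Section 12.2 says where an event is recorded, not how the endpoint is counted. The SAP, which was not available for this review, could draw on both record types.

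Several routes might also recover cases:

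- A deficiency noticed at surgery should be reported at the operative visit (Section 10.7), before any later AE exists. Section 12.5 then speaks of updating the original AE or DD form, and nothing tells the site to delete a DD record.
- An AE that occurs during surgery carries the index date.
- Deficiencies should also be noted in the medical record and the device returned if possible (Section 12.2). The sponsor reviews all AEs and DDs (Section 12.4.1), and product complaints are reported separately (Section 12.6).
- The eCRF itself is not shown, so a deficiency field may exist.

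Much of this stands. It narrows the clear exposure to deficiencies whose AE is already known when they are reported, and it means some cases could be recovered by review. It also confirms that the larger scenarios above are assumptions, and that the endpoint carries no hypothesis test.

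It does not remove the conflict. None of these routes is tied to the endpoint count. A SAP can combine the two sources only if the AE record identifies the deficiency and its day, and the protocol tells sites not to record these events as deficiencies. That instruction is fixed in the protocol; it is not a detail left open for the SAP.

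**Conclusion.** The concern holds, in conditional form: an index-day deficiency incidence taken from DD records may omit deficiencies that led to a subject AE. Any such bias is downward. Its size is unknown and could be near zero, because the protocol gives neither a MaxTack DD rate nor the share of deficiencies that lead to an AE. The one firm figure is 0.9 percentage points per affected subject, assuming 110 subjects and no other index-day deficiency in that subject.

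The consequence is limited to a descriptive secondary endpoint. The harm is still reported as an AE, and the primary endpoint, sample size and success rule are unaffected. It should be fixed, because the change is small and much easier to make during data collection than by searching AE descriptions afterwards.

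**What to change.** - **Section 12.2:** replace the sentence with a rule that every DD is recorded on the DD form with its date, whether or not an AE followed, and that any resulting AE is also recorded on the AE form and linked to the DD record.
- **Sections 5.2.2 and 14.5 (and the Synopsis to match):** state that DD incidence counts all subjects with at least one MaxTack deficiency on the index day, with or without an AE, and that the subset that led to an AE is reported separately.

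The cost is one sentence in Section 12.2, one in the endpoint and analysis text, and a link field on the existing eCRFs. The downsides are double entry for the few deficiencies that led to an AE and a possibly less favourable reported DD rate.

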12.3 Definitions/Classifications

Where the definition indicates "device", it refers to any device used in the study. This includes the MaxTack[™] Motorized Fixation Device and the mesh used during the procedure. All definitions and classifications are provided in Table 5: Adverse Event and Device Deficiency Definitions.

	General
Adverse Event (AE) (ISO14155:2020, 3.2)	Any untoward medical occurrence, unintended disease or injury, or untoward clinical signs (including abnormal laboratory findings) in subjects, users or other persons, whether or not related to the investigational medical device and whether anticipated or unanticipated. NOTE 1: This definition includes events related to the investigational medical device or the comparator. NOTE 2: This definition includes events related to the procedures involved. NOTE 3: for users or other persons, this definition is restricted to events related to the use of investigational medical devices or comparators.
Serious Adverse Event (SAE) (ISO 14155:2020, 3.45)	 Adverse event that led to any of the following: a) Death. b) Serious deterioration in the health of the subject, users or other persons as defined by one or more of the following: a life-threatening illness or injury, or a permanent impairment of a body structure or a body function including chronic diseases, or in-patient or prolonged hospitalization, or medical or surgical intervention to prevent life-threatening illness or injury, or permanent impairment to a body structure or a body function, or foetal distress, foetal death, a congenital abnormality, or birth defect including physical or mental impairment. NOTE: Planned hospitalization for a pre-existing condition, or a procedure required by the CIP, without serious deterioration in health, is not considered a serious adverse event.
Adverse Device Effect (ADE) (ISO14155:2020, 3.1)	Adverse event related to the use of an investigational medical device. NOTE 1: This definition includes adverse events resulting from insufficient or inadequate instructions for use, deployment, implantation, installation, or operation or any malfunction of the investigational medical device.

Table 5: Adverse Event and Device Deficiency Definitions

AFFIX (MaxTack[™] Motorized Fixation Device) Clinical Investigation Plan

MDT23014	Revision	3.0	Page 51 of 97	Medtronic	
	intentional misuse	e of the i	nvestigational medical	ng from use error or from device. rator is a medical device.	
Serious Adverse Device Effect (SADE) (ISO14155:2020, 3.44)	Adverse device ef characteristic of a		has resulted in any of adverse event.	the consequences	
Device Deficiency (DD) (ISO14155:2020, 3.19)	durability, reliabili NOTE 1: Device de inadequacy in the labeling. NOTE 2: This defir	ity, usabi eficiencie informa nition inc	evice with respect to it ility, safety, or perform is include malfunctions tion supplied by the m ludes device deficienci vice or the comparator	ance. s, use errors, and anufacturer including es related to the	
Serious Health Threat (SHT) (ISO14155:2020, 3.46)	imminent risk of d users or other per subjects, users or NOTE 1: This woul nature such that t	leath or a sons, an other pe ld include hey becc	d that requires prompt rsons. e events that are of sig	in the health in subjects, remedial action for other nificant and unexpected ential serious health hazard	
Relatedness					
investigators will use th	Each AE will be classified according to four different levels of causality. The sponsor and the investigators will use the following definitions to assess the relationship of the AE to the MaxTack™ motorized fixation device, mesh, or study procedure. For purposes of analysis categories considered "related" will include Possible, Probable and Causal.				
Not Related	or proced the event (if the respination implausib the discor level of activation creintroduc activation the event affected b the event concurrent	has no t ure does no ponse pa le ntinuatio ctivation, ction of i /exposu involves oy the de can be a at illness,	emporal relationship w t follow a known respo attern is previously kno n of device application dexposure - when clinic ts use (or increase of the re), do not impact on the a body-site or an orga vice or procedure ttributed to another ca	or the reduction of the cally feasible – and he level of he event	

AFFIX (MaxTac Clinical Investi				
MDT23014	Revision	3.0	Page 52 of 97	Medtronic

	 the event does not depend on a false result given by the device used for diagnosis, when applicable In order to establish the non-relatedness, not all the criteria listed above might be met at the same time, depending on the type of device/procedures and the event. The relationship is weak but cannot be ruled out completely. Alternative 					
Possible	causes are also possible (e.g., an underlying or concurrent illness/ clinical condition or/and an effect of another device, drug or treatment). Cases where relatedness cannot be assessed or no information has been obtained should also be classified as possible.					
Probable	The relationship seems relevant and/or the event cannot reasonably be explained by another cause.					
Causal Relationship	 The event is associated beyond reasonable doubt when: the event is a known side effect of the product category the device belongs to or of similar devices and procedures the event has a temporal relationship with device use/application or procedures the event involves a body-site or organ that the event involves a body-site or organ that the device or procedures are applied to the device or procedures have an effect on the event follows a known response pattern to the device (if the response pattern is previously known) the discontinuation of device application (or reduction of the level of activation/exposure) and reintroduction of its use (or increase of the level of activation/exposure), impact on the event (when clinically feasible) other possible causes (e.g., an underlying or concurrent illness/ clinical condition or/and an effect of another device, drug or treatment) have been adequately ruled out harm to the subject is due to error in use the event depends on a false result given by the device used for diagnosis, when applicable In order to establish the relatedness, not all the criteria listed above might be met at the same time, depending on the type of device/procedures and the event. 					
Unavoidable Adverse Events (UAE)	For study purposes, the following unavoidable adverse event (UAE) occurrences are considered to be expected observations following surgical procedures (primarily associated with anesthesia) and will not be considered reportable AEs, as long as the event is not associated with significant sequelae, does not prolong hospitalization, and responds to standard medical therapy:					

AFFIX (MaxTac Clinical Investig		d Fixa	tion Device)			
MDT23014	Revision	3.0	Page 53 of 97	Medtronic		
	 Postoperative transient nausea determined to be procedure related within the first 24 postoperative hours. Postoperative transient emesis determined to be procedure related within the first 24 postoperative hours. Postoperative constipation determined to be procedure and/or medication related for the duration of medication administration for management of pain. Postoperative pain that the Investigator considers common and within normal limits for the procedure and is well-managed with medication. 					
	Device/	Procedu	re Relatedness			
Study Device Related	An AE that results from the presence or performance (intended or otherwise) of the MaxTack™ Motorized Fixation Device.					
Mesh Related	An AE that results from the presence or performance (intended or otherwise) of the mesh.					
Study Procedure Related	fixation methods,	, skin clo	sure, etc.) related to t	nesthesia, incision, other he implantation or surgical ion Device, or the mesh.		

